4.1 Analysis Populations

All safety analyses will be based on the Safety Population, which includes all participants who receive at least 1 dose of study drug.

All PK analysis will be based on the PK Population, which includes all participants who receive any amount of ARN-75039 in either formulation and have sufficient data to be included in the PK analysis post-dose concentration-time data to determine at least 1 PK parameter.

Any participant with pre-dose concentrations of ARN-75039 will be presented in the individual plasma concentration and PK listings but excluded from summary plasma concentrations, and PK summary table descriptive statistics if the pre-dose concentration is greater than 5% of the C_{\max} value for that participant of that same period.

Participants who vomit within 4 hours post-dose will be excluded from PK statistical analysis for that period.

The frequency and percentage of participants in each population will be summarized. The listing will include all participants.

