### 3.2. Justification for the Study Design

A randomized, comparative, crossover study was selected to eliminate participant variation and to improve precision of the PK characteristics of both study drug formulations with a smaller sample size. To compensate for the long half-life of the study drug and the relatively short washout period, additional PK timepoints were included to aid in modeling of the study drug clearance and elimination.

This clinical study is being performed in healthy participants to avoid interference with the results from disease processes and other drugs. Medications, substances, and food products that may interfere with the assessment of the PK profile of ARN-75039 are prohibited during study participation.

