Written informed consent for study participation will be obtained before any study-related procedures or assessments are performed. All potential participants will be screened for potential participation, and those meeting all eligibility criteria will be offered participation in the study.

Participants will be admitted to the study site on the morning of Day -1, randomized to sequence of study drug administration on Day 1, and will remain on site until study completion at Day 15. Participants will receive the randomized study drug in the morning following a standardized meal. Participants will be dosed on Day 1 and Day 8 with a 7-day wash out period between the two dosing days. Pharmacokinetic (PK) assessments will be performed according to the Schedule of Assessments (SOA) ([Table 1](#)).

Table 1: Schedule of Assessments

Procedure	Period	Screening Period	Admission	Period 1						Period 2								End of Active Treatment		Follow Up Phone Call
	Visit	Screening	P1D-1	P1D1	P1D2	P1D3	P1D4	P1D5	P1D6	P2D-1	P2D1	P2D2	P2D3	P2D4	P2D5	P2D6	P2D7	Discharge	ET	Day 36 +/- 2 days
	Study Day	Days -21 to -1	-1	1	2	3	4	5	6	7	8	9	10	11	12	13	14	15	ET ^a	
Informed consent		X																		
Eligibility criteria review		X	X																	
Randomization				X																
Demographics ^b		X																		
Medical and surgical histories		X	X																	
Vital signs ^c		X	X	X	X	X	X	X	X	X	X	X	X	X	X	X	X	X	X	
Physical examination ^d		X			X							X						X	X	
Pregnancy test ^e		X	X															X	X	
Concomitant medications		X	X															X	X	
Adverse events				X	X	X	X	X	X	X	X	X	X	X	X	X	X	X	X	X

Procedure	Period	Screening Period	Admission	Period 1						Period 2								End of Active Treatment		Follow Up Phone Call
	Visit	Screening	P1D-1	P1D1	P1D2	P1D3	P1D4	P1D5	P1D6	P2D-1	P2D1	P2D2	P2D3	P2D4	P2D5	P2D6	P2D7	Discharge	ET	Day 36 +/- 2 days
	Study Day	Days -21 to -1	-1	1	2	3	4	5	6	7	8	9	10	11	12	13	14	15	ET ^a	
12-lead ECG ^f		X	X	X	X	X	X			X	X	X	X	X				X	X	
Hematology ^g		X	X		X					X		X						X	X	
Drug test (urine) alcohol test (breath)		X	X																	
Serology ^h		X																		
Serum chemistry and coagulation ^g		X	X		X					X		X						X	X	
Urinalysis ^g		X			X							X						X	X	
Admission to site			X																	
Study drug administration				X							X									
PK (plasma) ⁱ				X	X	X	X	X	X	X	X	X	X	X	X	X	X	X	X	
Discharge from site																		X	X	

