- ^f Triplicate ECGs will be performed at screening, admission, dosing Day 1 in each period, and end of treatment (discharge or early termination). Triplicate ECGs will be measured at pre-dose (within -90min), and post dose 1hr (± 20 min), 3hr (± 20 min), 6hr (± 20 min), 8hr (± 20 min), 24 hr (± 60 min), 48 hr (± 60 min), and 72 hr (± 60 min) post dose (for both doses) triplicates measurement will be taken within 5 minutes apart. Subjects should be at rest for 10 minutes prior to ECG. For participants that withdraw or are terminated early from the study, ECG will be performed at the ET visit.
- ^g Samples must be collected following a minimum 8 hours fast.
- ^h Serology includes HbsAg, anti-HCV Ab, and anti-HIV Ab.
- ⁱ PK assessments should be performed on Day 1 of Periods 1 and 2 Pre-dose (hour 0) (within 60 mins prior to dosing), 0.5 hour (± 2 mins), 1 hour (± 5 mins), 2 hours (± 5 mins), 3 hours (± 10 mins), 4 hours (± 10 mins), 6 hours (± 10 mins), 8 hours (± 10 mins), 10 hours (± 10 mins), 12 hours (± 10 mins), 24 hours (± 60 mins), 48 hours (± 60 mins), 72 (± 60 mins), 96 (± 60 mins), 120 (± 60 mins), 144 (± 60 min), and 168 hours (± 60 mins) relative to morning dose and at Discharge or ET visit at approximately the same time (± 1 hr) as the dose of study drug administration. The 168-hour post-dose PID1 may be combined with the pre-dose PK collection for P2D1. P2D7 PK will be collected 144 (± 60 min).

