For the above comparison confidence intervals (CIs; 90%) will be constructed to test the two one-sided hypotheses at the $\alpha = 0.05$ level of significance for C_{\max} , AUC_{0-t} , and $AUC_{0-\infty}$. Natural log-transformed PK parameters C_{\max} , AUC_{0-t} , and $AUC_{0-\infty}$ data will be analyzed using an analysis of variance (ANOVA) model with fixed effects for treatment, period and sequence, and a random effect of subject nested in sequence. This may be an unbalanced model due to possible subject differences between PK parameters reported by treatment.

The relative bioavailability will be established if the 90% CI for the ratio of the population geometric means between comparator and reference product, based on natural log-transformed data, is contained within the equivalence limits of 80.00-125.00% for C_{\max} , AUC_{0-t} , and $AUC_{0-\infty}$ (if applicable).

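### As written, the 5% pre-dose rule stops at the descriptive tables and nothing removes residual drug from Period 2, so carry-over can bias the tablet/capsule ratio in the ANOVA

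*SAP*

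**What the plan says.** Protocol 3.2 gives the reason for the extended sampling: "To compensate for the long half-life of the study drug and the relatively short washout period". The remedy it names is extra sampling times, meant to support modelling of how the drug is cleared. On the schedule, SAP Section 3 states: "Participants will be dosed on Day 1 and Day 8 with a 7-day wash out period between the two dosing days". The footnote on PK sampling in the SAP schedule of assessments lets the 168-hour Period 1 sample double as the Period 2 pre-dose sample.

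SAP 4.1 contains the only rule on residual drug. A participant with pre-dose drug is kept in the listings but "excluded from summary plasma concentrations, and PK summary table descriptive statistics if the pre-dose concentration is greater than 5% of the" Cmax of the same period. The sentence that follows uses wider wording: "Participants who vomit within 4 hours post-dose will be excluded from PK statistical analysis for that period".

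SAP 4.6 plans non-compartmental analysis (NCA) on observed concentrations. It reports lambda_z, half-life and CL/F, and has no step that corrects Period 2. The comparison uses an "analysis of variance (ANOVA) model with fixed effects for treatment, period and sequence, and a random effect of subject nested in sequence", and the 90% CI is compared with 80.00-125.00% for Cmax, AUC0-t and, if applicable, AUC0-inf.

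**The concern.** The two adjacent rules in SAP 4.1 differ in scope. The vomiting rule removes data from the statistical analysis; the pre-dose rule names only summary concentrations and descriptive statistics. A programmer following the text would drop a flagged Period 2 profile from the tables and keep it in the ANOVA, so the two outputs would rest on different data.

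Residual drug adds to Period 2 exposure. The period effect absorbs it only if it raises log exposure equally in both sequences. If one formulation gives higher exposure, it leaves more residue, and that residue is counted for the other formulation. The quantity at risk is the ratio on which the SAP's equivalence criterion is judged.

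The unit of exclusion is also unclear: the rule is worded by participant, whereas the vomiting rule is worded by period.

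**Working it through.** **Inputs from the documents.** Dosing interval 168 h (SAP Section 3); 16 participants, 1:1, so 8 per sequence (SAP Section 3); model, 90% CI and limits (SAP 4.6); 5% of same-period Cmax (SAP 4.1); AUC0-inf withheld if more than 20% is extrapolated (SAP 4.6).

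**Assumptions.** The documents give no human half-life, within-subject CV or expected ratio. I assume linear kinetics, half-lives of 24 to 96 h and within-subject CVs of 15% to 30%. The sample size was not calculated, so there is no planned figure to reproduce.

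**Step 1: carried fraction.** With mono-exponential decay, AUC from 168 to 336 h divided by AUC from 0 to 168 h is f = 2^(-168/t½).

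**Step 2: what the crossover estimates.** Set capsule exposure to 1 and tablet exposure to R. Let fR and fT be the fractions carried over from capsule and tablet. The estimate is

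R_hat = sqrt[ R(R + fR) / (1 + fT·R) ].

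Example at 48 h: f = 2^(-3.5) = 0.0884. For R = 1.25, R_hat = sqrt(1.25 × 1.3384 / 1.1105) = 1.2274.

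| Assumed t½ (h) | f | True 0.80 | True 1.00 | True 1.25 |
|---|---|---|---|---|
| 24 | 0.8% | 0.8014 | 1.000 | 1.2478 |
| 48 | 8.8% | 0.8147 | 1.000 | 1.2274 |
| 72 | 19.8% | 0.8303 | 1.000 | 1.2045 |
| 96 | 29.7% | 0.8421 | 1.000 | 1.1875 |

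The columns use fR = fT = f. Simulated oral profiles at the scheduled times, analysed by linear-up/log-down NCA, gave AUC0-t estimates of 1.227 (48 h) and 1.204 (72 h) for a true 1.25.

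**Step 3: direction.** With unequal fractions the bias can go the other way. For R = 1 with fR = 10% and fT = 5%, R_hat = sqrt(1.10/1.05) = 1.024. For R = 1.25 with fR = 15% and fT = 5%, R_hat = sqrt(1.25 × 1.40 / 1.0625) = 1.283.

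**Step 4: effect on the test.** Simulated two one-sided tests for a single parameter at a true ratio of 1.25, n = 16, 14 df:

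| Assumed CV | No carry-over | 48 h | 72 h | 96 h |
|---|---|---|---|---|
| 15% | 5% | 9% | 16% | 24% |
| 20% | 5% | 8% | 13% | 17% |
| 30% | 4% | 6% | 8% | 10% |

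**Step 5: what the 5% screen catches.** In the mono-exponential case, Period 2 pre-dose over same-period Cmax is f/(1+f). This exceeds 5% when f > 1/19, that is t½ > 168·ln 2/ln 19 = 39.5 h.

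The screen does not bound AUC contamination. Assume 80% of the initial concentration declines with a 6 h half-life and 20% with 72 h. The 168 h concentration is 0.2 × 0.1984 = 0.0397, about 4% of Cmax, so the profile passes. In units of 1/ln 2, the carried AUC is 14.4 × 0.1984 × 0.8016 = 2.290 and AUC0-168 is 4.8 + 14.4 × 0.8016 = 16.343. The inflation is 2.290/16.343 = 14%.

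**Step 6: exclusion as the only remedy.** If every Period 2 profile is flagged, 8 versus 8 remain in Period 1. Simulated power at a true ratio of 1 is then about 39%, 4% and 0.3% at assumed total CVs of 20%, 30% and 40%. The full crossover has about 83%, 57% and 32% at within-subject CVs of 20%, 25% and 30%.

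**The case against.** The strongest reply is that the rule's reach is unstated, and that retention in the ANOVA is inferred from silence. SAP 4.6 does expect a possibly unbalanced model, so some profiles may drop out. That sentence, however, refers to which parameters are reported by treatment and does not mention the pre-dose rule. The contrast with the vomiting sentence favours the literal reading. Even on the kinder reading, the SAP needs to say which applies.

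Three other points limit the claim:

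- **Size.** At 24 h the effect is negligible. Above about 72.4 h (168·ln 2/ln 5, mono-exponential) more than 20% of AUC is extrapolated and AUC0-inf is withheld, although AUC0-t and Cmax remain exposed.
- **Yardstick.** The criterion is the whole 90% CI, so a point estimate moving inside the limits is not a finding of equivalence. The error rates in Step 4 are the relevant measure. They are for one parameter; passing all parameters jointly cannot be more likely.
- **Weight.** The protocol synopsis calls the primary analysis descriptive and the sample size was not statistically based. Still, the SAP attaches a formal 80.00-125.00% criterion, and the ratio should be sound for it.

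A reader might infer that the protocol expects carry-over and promises modelling that was then dropped. It does not go that far: it flags the two conditions and says the added samples help modelling, and the SAP does estimate lambda_z, half-life and CL/F. What is missing is their use to correct Period 2.

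**Conclusion.** The point holds. As written, the 5% rule covers descriptive outputs only, neither the NCA nor the ANOVA deals with residual drug, and contaminated Period 2 profiles stay in the equivalence test.

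The consequence is a possible bias of uncertain size. With equal carry-over fractions, a true AUC ratio of 1.25 is understated by less than 0.2% at an assumed 24 h half-life (1.2478) and by 5% at 96 h (1.1875/1.25 = 0.95). At CV 20%, the error rate at that boundary rises from 5% to about 17% at 96 h.

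It would be tempting to say that the bias always favours equivalence. The documents do not support that: it depends on similar carry-over fractions, vanishes at a true ratio of 1, and can reverse. Half-life, CV and the bi-exponential shape are all assumptions. An unknown direction is itself a reason to settle the handling before the pre-dose data are seen.

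**What to change.** **SAP 4.1.** State that wherever the 5% rule is used, it removes the same participant-periods from the ANOVA as from the tables, by period and not by participant.

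**SAP 4.6.** When the Period 2 pre-dose concentration (C_pre) is quantifiable, subtract C_pre × exp(-lambda_z,Period 1 × t) from that participant's Period 2 concentrations before NCA, with t the time since the Period 2 dose. State a fallback, such as the Period 2 or a pooled lambda_z, for participants whose Period 1 value is not reportable under the SAP's own criteria. Use the corrected parameters in both tables and ANOVA, so that the 5% exclusion becomes a sensitivity analysis. Report uncorrected, 5%-excluded and Period-1-only results as sensitivity analyses.

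**Cost.** SAP wording and modest programming; the samples are already scheduled. Individual lambda_z estimates add some noise. The exclusion analysis may lose much precision if many Period 2 profiles are flagged (Step 6), so exclusion should not be the only remedy.

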4.2 Study Participants

All safety summary tables will be presented as specified in the sections outlined below. All safety listings will include all subject data.

Disposition

Disposition will be summarized for the randomized participants by the following: using the number and percent of participants who complete the study; the number and percent of participants who discontinue the study; the reasons for discontinuation by treatment sequence; and Total. Eligibility status, disposition, and completion status will be listed for all randomized participants.

Protocol Deviations

Protocol deviations will be identified prior to database lock and may include but are not limited to: inclusion/exclusion violation; use of restricted medication; or not following clinical trial protocol procedures (includes: assessment not performed per protocol; assessment performed outside window, missed assessment, missed visit, PK draw not performed, PK draw performed outside window) that may affect evaluation of PK profile.

Protocol deviations will be listed by participant, treatment, and treatment sequence.

4.3 Demographics/Other Baseline Characteristics

Demographic and baseline characteristics will be summarized by treatment sequence for all participants in the safety population. The demographic and baseline characteristics will consist of age, sex, race, ethnicity, height (cm), weight (kg), body mass index (BMI) (kg/m^2).

All demographic information will be summarized by treatment sequence and overall (across sequences).

Individual demographic and baseline characteristics for the safety population will be listed by participant and treatment sequence.

Age is a calculated parameter. Age will be calculated using the participant's date of birth (date of birth is not included in the database) and the participant's informed consent date.

Continuous variables (age, height, weight, BMI) will be summarized by n, mean, SD, min, median, and max. Number of participants and percentages will be used to describe categorical (discrete) variables (gender, race, and ethnicity).

4.4 General Medical/Surgical History and Procedures/Non-Drug Therapies

Any current medical conditions and/or other significant medical/surgical history will be coded using Medical Dictionary for Regulatory Activities (MedDRA) version 25.1 or higher. Any procedures/non-drug therapies that are incurred during the course of the study will also be coded using MedDRA. Medical/surgical history will be listed by subject. Procedures/non-drug therapies will be listed by subject, treatment, and treatment sequence.

4.5 Prior and Concomitant Medications

All prescription and over-the-counter (OTC) medications, herbals, and supplements taken by participants during the study (i.e., from signing the informed consent form (ICF) through the Day 15 visit) must be documented on the source document and transcribed into the eCRF.

Any medications prohibited in the protocol should not be allowed and will result in the subject being violated by protocol for the PK population. Refer to the protocol for any additional information.

Prior and concomitant medications will be recorded and coded using the current version of WHO Drug Enhanced Dictionary (Global B3 September 2024 or higher). Prior medications will be those that start and end prior to the first dose of study drug.

Concomitant medications will be those that have a known end date after the first dose of study drug or have a missing end date. Any concomitant medication taken during the washout period will be assigned to the prior treatment given. Anatomical Therapeutic

Chemical (ATC) classification and Preferred Term will be assigned to each record of prior or concomitant medication. All prior and concomitant medications will be listed by subject and by treatment sequence (both prior and concomitant), and treatment (for concomitant), including ATC classification (level 3), preferred term and reported term, the start and end dates (or ongoing status), dose, unit, frequency, route of drug administration, and indication. All concomitant medications administered will be presented in a data listing.

4.6 Pharmacokinetic Analysis

Pharmacokinetic analyses will be performed for each participant in the PK population. Blood samples will be collected and resulting plasma analyzed to obtain plasma concentrations. The plasma concentration data will be listed at actual and nominal time points by participant. Plasma concentrations will be summarized by treatment at each nominal time point of plasma collection using descriptive statistics (n, mean, SD, CV%, geometric mean, geometric CV%, median, min, and max values), and listed by participant, treatment, sequence and with both nominal and actual plasma collection point.

For plasma concentration data, all values below the quantification limit (BQL) will be labeled as such in the concentration listings and treated as zero for the concentration data summary statistics and mean summary figures.

For PK parameter calculations, concentrations BQL will be set to zero if they occur prior to the first quantifiable concentration and after the last quantifiable concentration. The BQL values in between measurable plasma concentrations will be set to missing.

The plasma PK parameters for ARN-75039 will be estimated by non-compartmental analysis (NCA) methods using Phoenix WinNonlin (version 8.1 or higher, Certara USA Inc., Princeton, NJ, USA) and will be based on actual individual time since dosing of blood sample collection.

The following PK parameters will be computed at minimum from plasma concentration data:

C_{\max}	maximum plasma concentration
$C_{\min 0-24}$	observed plasma concentration from time zero to 24 hours post-dose
t_{\max}	time of maximum plasma concentration
$\lambda_z (k_{el})$	terminal-phase rate constant
$t_{1/2}$	elimination half-life
AUC_{0-24}	area under the plasma concentration-time curve from time zero to 24 hours post-dosing
AUC_{0-t}	area under the plasma concentration-time curve from time zero to time t (time of last quantifiable plasma concentration)

$AUC_{0-\infty}$	area under the plasma concentration-time curve from time zero to infinity
CL/F	apparent clearance
MRT	mean residence time
V_z/F	apparent volume of distribution

The C_{max} and t_{max} will be obtained directly from the experimental observations and AUC_{0-t} will be estimated using the Linear up – Log down trapezoidal method from time 0 hour to last observed concentration hour.

$AUC_{0-\infty}$ will be calculated as the sum of AUC_{0-t} and $AUC_{t-\infty}$, where t is the time corresponding to the last measurable plasma concentration (t_{last}). $AUC_{t-\infty}$ is defined as the area under the curve from last measurable concentration estimated to infinity and is calculated by C_{last} (plasma concentration at the last quantifiable time point) divided by terminal elimination rate constant (K_{el}). $AUC_{t-\infty}$ will not be an included PK parameter in the listings or tables.

No values for λ (K_{el}), $AUC_{0-\infty}$, CL/F , V_z/F , or $t_{1/2}$ will be reported for cases that do not exhibit a terminal log-linear phase in the concentration-time profile with at least three timepoints past t_{max} (typically this would be at least the last 3 quantifiable data points representing the terminal elimination phase).

If R-squared adjusted is <0.80 , the PK analyst may evaluate whether other time points are more appropriate for the calculation of λ (K_{el}), otherwise λ (K_{el}) and PK parameters derived with λ (K_{el}) such as $t_{1/2}$ and $AUC_{0-\infty}$, will not be reported. R-square adjusted values will be reported in a listing and in the dataset.

For determination of $AUC_{0-\infty}$, if calculated $AUC_{t-\infty}$ is greater than 20% of the calculated AUC from time 0 to infinity, then $AUC_{0-\infty}$ and those PK parameters derived from $AUC_{0-\infty}$ will not be reported. $AUC_{inf\%}$ extrapolation values will be reported in a listing and in the dataset.

Pharmacokinetic parameters will be listed by participant, treatment sequence, and treatment for all participants in the PK population. Pharmacokinetic parameters will be summarized by treatment using descriptive statistics (n, mean, SD, CV%, geometric mean, geometric CV%, median, min, and max values), except for t_{max} which will be described using min, median, and max.

Relative Bioavailability Analysis

The relative bioavailability of ARN-75039 for capsule versus tablet formulation will be evaluated as follows

- Relative Bioavailability of 300 mg ARN-75039 with excipients in tablet form (Treatment B, comparator) versus 300 mg neat ARN-75039 in HPMC capsules (Treatment A, reference product)

For the above comparison confidence intervals (CIs; 90%) will be constructed to test the two one-sided hypotheses at the $\alpha = 0.05$ level of significance for C_{\max} , AUC_{0-t} , and $AUC_{0-\infty}$. Natural log-transformed PK parameters C_{\max} , AUC_{0-t} , and $AUC_{0-\infty}$ data will be analyzed using an analysis of variance (ANOVA) model with fixed effects for treatment, period and sequence, and a random effect of subject nested in sequence. This may be an unbalanced model due to possible subject differences between PK parameters reported by treatment.

The relative bioavailability will be established if the 90% CI for the ratio of the population geometric means between comparator and reference product, based on natural log-transformed data, is contained within the equivalence limits of 80.00-125.00% for C_{\max} , AUC_{0-t} , and $AUC_{0-\infty}$ (if applicable).

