2.3 Endpoints

Primary:

- Relative bioavailability comparison of 300 mg neat ARN-75039 in HPMC capsules (Treatment A; reference) to 300 mg ARN-75039 with excipients tablets (Treatment B; comparator) following oral administration under fed conditions.
- PK parameters of 300 mg ARN-75039 with excipients tablets and 300 mg neat ARN-75039 in HPMC capsules, including but not limited to:
 - Area under the plasma concentration-time curve from time zero to time of last quantifiable concentration (AUC_{0-t}).
 - Area under the plasma concentration-time curve from time zero to 24 hours post-dose (AUC_{0-24}).
 - Area under plasma concentration-time curve from time zero to infinity ($AUC_{0-\infty}$).
 - Maximum observed plasma concentration (C_{max}).

- Minimum observed plasma concentration from time zero to 24 hours post-dose $C_{min0-24}$.
- Time to reach C_{max} (t_{max}).
- Half-life ($t_{1/2}$).
- Apparent clearance after extravascular administration (CL/F).
- Apparent volume of distribution during the terminal phase after extravascular administration (V_z/F).

Secondary:

- Type and frequency of treatment-emergent adverse events (TEAEs).
- Type and frequency of treatment-emergent serious adverse events (TESAEs).
- Type and frequency of study drug-related >Grade 1 TEAEs.
- Type and frequency of changes in clinical laboratory values, ECGs, colonic transit time (biomarker), physical examinations, and vital signs.

3 Study Design and Methods

ARN-75039-103 is a comparative, randomized, single-dose, crossover study to assess the PK, safety, and tolerability of neat ARN-75039 in hydroxypropyl methylcellulose (HPMC) capsules against ARN-75039 with excipients in tablet form administered by the oral route in healthy adult participants. The safety assessments will include assessments of vital signs, clinical laboratory values, and ECGs.

A total of 16 participants were randomized 1:1 into one of the following two sequences:

Sequence 1:

[figure not shown]
- Period 1: 300 mg neat ARN-75039 in HPMC capsules (Treatment A; reference product)
- Period 2: 300 mg ARN-75039 with excipients in tablet form (Treatment B; comparator)

Sequence 2:

- Period 1: 300 mg ARN-75039 with excipients in tablet form (Treatment B; comparator)
- Period 2: 300 mg neat ARN-75039 in HPMC capsules (Treatment A; reference product)

A study scheme is provided below:

Sequence 1

Sequence 2

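### AUC0-24 and Cmin0-24 are primary endpoints of a formulation comparison, but the SAP plans no formulation ratio or confidence interval for either

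*SAP*

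**What the plan says.** The primary objective in the Protocol (Synopsis and section 2) and in SAP 2.1 is to compare the pharmacokinetics of the two formulations. The primary endpoints in SAP 2.3 include "Area under the plasma concentration-time curve from time zero to 24 hours post-dose" and the minimum concentration over the same 24 hours. The Protocol Synopsis lists both. Protocol section 2 does too, although it prints the symbol for the minimum as a Cmax.

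SAP 4.6 computes both parameters. Its relative bioavailability analysis, however, names three others. For Cmax, AUC0-t and AUC0-infinity, "confidence intervals (CIs; 90%) will be constructed to test the two one-sided hypotheses at the" 0.05 level, and the log-transformed values "will be analyzed using an analysis of variance (ANOVA) model with fixed effects for treatment, period and sequence", with participant within sequence as a random effect. Relative bioavailability is taken as established if the 90% CI "is contained within the equivalence limits of 80.00-125.00% for" those three, AUC0-infinity only where applicable.

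For the other parameters SAP 4.6 plans listings by participant and descriptive statistics by treatment, including geometric mean and geometric CV. Protocol 7.9 plans descriptive tabulation only.

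**The concern.** Two named primary endpoints of a comparative trial have no planned comparative estimate. Protocol 3.2 justifies the crossover by its removal of participant variation and its gain in precision. A summary by treatment does not use that pairing and attaches no interval to the difference between formulations.

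These two metrics also link the trial to its own background data. The dog comparison of tablet and capsule (Protocol Table 2) is reported as Cmax, AUC0-24 and the 24-hour concentration. Of these, only Cmax will have a human ratio with an interval under the present plan. What is at stake is how completely the primary objective is answered; no error rate is affected.

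**Working it through.** **Coverage of the primary endpoints**
- Cmax, AUC0-t: model, 90% CI and equivalence rule.
- AUC0-infinity: the same, if reportable.
- AUC0-24, Cmin0-24: descriptive by treatment only.
- tmax, t1/2, CL/F, Vz/F: descriptive only.

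**The plan's own figure.** Two one-sided tests at 0.05 correspond to a CI level of 1 − 2 × 0.05 = 0.90, which agrees with the SAP. The sample size of 16 is stated not to come from a calculation (SAP 3.3), so there is no power figure to reproduce.

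**Why these two metrics matter here.** Dog ratios, prototype 5 tablet to capsule, from Protocol Table 2: AUC0-24 42542/45453 = 0.94; 24-hour concentration 399/369.1 = 1.08; Cmax 5346/4518 = 1.18.

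**Precision if the endpoint enters the same model.** Inputs: N = 16 with 8 per sequence (SAP section 3), and an assumed within-participant CV.
- s_w = sqrt(ln(1 + CV²)); SE = s_w × sqrt(2/N); df = N − 2.
- CI factor = exp(t(0.95, df) × SE), with t(0.95, 14) = 1.761 and sqrt(2/16) = 0.3536.
- CV 20%: s_w = 0.198, factor exp(0.123) = 1.131, or 88.4 to 113.1% around a ratio of 100%.
- CV 30%: s_w = 0.294, factor 1.201, or 83.3 to 120.1%.
- CV 40%: s_w = 0.385, factor exp(0.240) = 1.271, or 78.7 to 127.1%.
- With only 12 complete pairs the factors are 1.158 at CV 20% and 1.330 at CV 40%.

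**Why estimation only.** If AUC0-24 also had to meet 80.00 to 125.00%, its own power at a true ratio of 1.00 with 16 pairs would be 0.83 at CV 20%, 0.33 at CV 30% and 0.07 at CV 40%. Adding it to the rule would not inflate type I error, but could lower the chance of meeting the rule. As an estimate outside the rule it changes no error rate.

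**Cmin0-24.** The pre-dose sample is hour 0, and prior exposure to the drug is an exclusion criterion, so Period 1 pre-dose values should be below quantification. SAP 4.6 sets such values to zero when they precede the first quantifiable concentration. Read literally, the minimum from time zero is then zero in Period 1, and its logarithm does not exist. The planned geometric mean meets the same problem. An early post-dose sample below quantification would have the same effect.

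**Exclusions.** SAP 4.1 drops a participant from the PK summary statistics when the pre-dose level exceeds 5% of that period's Cmax, and drops a period from PK statistical analysis after vomiting within 4 hours. Assume one-phase decline, ignore absorption time, and let r be the fraction remaining at 168 h. The Period 2 pre-dose share of Cmax is then r/(1 + r), which exceeds 5% once r > 1/19, that is, at a half-life above 168 × ln 2/ln 19 = about 40 h. The documents give no human half-life.

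**The case against.** The strongest reply is that descriptive handling was intended. The Protocol Synopsis says the primary analysis will describe the PK characteristics, and Protocol 7.9 tabulates every parameter descriptively. SAP 2.3 lists the relative bioavailability comparison and the PK parameters as separate primary items, and the second list also holds tmax, half-life, CL/F and Vz/F, which nobody expects to be tested. That is a fair reading, but the SAP does not state it, and the primary objective is comparative.

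A second reply is that a ratio can be formed by hand. This stands in part. Geometric means are tabulated wherever they can be calculated, and with all 16 participants complete, 8 per sequence, their ratio equals the model's point estimate. Individual values are also listed. What is missing is a planned interval and, once data are unbalanced, the period adjustment.

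A reader might go further and infer that the conclusion could rest on AUC0-t alone, because AUC0-infinity is withheld when the extrapolated part "is greater than 20% of the calculated AUC from time 0 to infinity". The documents do not support this. Cmax stays in the model and in the rule, so at worst AUC0-t is the only AUC. Under one-phase decline with the last sample at 168 h, the 20% limit is crossed at a half-life of 168 × ln 2/ln 5 = about 72 h. Protocol 3.2 says only that the half-life is long, so this loss is possible but not shown to be likely.

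Nor would AUC0-24 be a good substitute in that case. At a 72 h half-life it covers 1 − exp(−ln 2 × 24/72) = 21% of total exposure, against about 80% up to 168 h. The Period 2 pre-dose level would be about 0.198/1.198 = 17% of Cmax, beyond the 5% rule, so 16 clean pairs could not be assumed either. The case for including AUC0-24 is its status as a primary endpoint, not protection against a long half-life.

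**Conclusion.** The omission stands on the text and needs no calculation: AUC0-24 and Cmin0-24 are primary endpoints under a comparative objective, and no modelled ratio or interval is planned for either. It is a gap in reporting. The three-parameter rule, its limits and its error rates are sound as written on this point.

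The gain from closing the gap is a 90% CI with a factor of about 1.13 to 1.27 for an assumed within-participant CV of 20 to 40%. This rests on 16 complete pairs and log-normal data, and it widens if periods are excluded. For Cmin0-24 the figure applies only once the parameter is defined so that it is positive in both periods.

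**What to change.** In SAP 4.6, add ln(AUC0-24) and ln(Cmin0-24) to the same ANOVA and report each geometric mean ratio, tablet to capsule, with its 90% CI. Label both as estimation only, outside the 80.00 to 125.00% rule.

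Before log-transforming Cmin0-24, state how it is derived (for example, from post-dose samples or as the 24-hour concentration) and how any remaining zero is handled. Taking only the non-zero values under the present definition could leave few or no Period 1 values. State also whether the 5% pre-dose exclusion in SAP 4.1 applies to the model as well as to the summaries, and correct the misprinted symbol in Protocol section 2.

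If the sponsor prefers descriptive handling, one sentence in SAP 4.6 saying so would settle the ambiguity, though it would forgo the intervals.

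The cost is two model runs, two table rows and a definition, with no new data and no change to the decision rule: a free improvement. The one drawback is two further intervals that may not agree with the other three, which the label covers. If the SAP is already final, SAP 4.10 gives the route for documenting the change.
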